5 PROCEDURES

This clinical investigation will be conducted in accordance with this CIP. All parties involved in the conduct of this clinical investigation will be qualified by education, training, or experience to perform their tasks and this training will be documented appropriately.

This clinical investigation will not commence until the Sponsor receives written approval from the Institutional Review Board (IRB) and all required documents have been collected from the investigational site(s). All study staff will be required to undergo training prior to performing any study related activities. Approval from the Sponsor must be received and patients must sign written informed consent prior to initiating study procedures.

The following sections provide a detailed description of procedures required by this CIP.

5.1 PATIENT RECRUITMENT

Patients will be recruited for the study by reviewing the device database for HeartMate LVAS patients with CardioMEMS devices for appropriateness for inclusion. Due to the narrow inclusion criteria requiring two specific devices, no additional steps will be taken to recruit under represented populations.

5.2 INFORMED CONSENT PROCESS

The Principal Investigator or his/her authorized designee will conduct the Informed Consent Process, as required by applicable regulations and the center's IRB. Patients from Group A will provide consent for the sponsor to access CardioMEMS historical data collected prior to study enrollment as well as current data from the Merlin.net website. Group B will provide consent to review all data collected in the study. The CardioMEMS sensor must be implanted within 72 hours of consent.

This informed consent process will include a verbal discussion with the subject on all aspects of the clinical investigation that are relevant to the subject's decision to participate, such as details of clinical investigation procedures, anticipated benefits, and potential risks of clinical investigation

This confidential document is the property of Abbott and shall not be reproduced, distributed, disclosed or used without the express written consent of Abbott.

participation. During the discussion, the Principal Investigator or his/her authorized designee will avoid any improper influence on the subject and will respect the subject's legal rights. The subject shall be provided with the informed consent form written in a language that is understandable to the subject and has been approved by the center's IRB. The subject shall have adequate time to review, ask questions and consider participation.

If the subject agrees to participate, the Informed Consent form must be signed and dated by the subject and by the person obtaining the consent. The signed original will be filed in the subject's hospital or research charts, and a copy will be provided to the subject.

Failure to obtain informed consent from a subject prior to clinical investigation enrollment should be reported to Sponsor within 5 working days and to the reviewing center's IRB according to the IRB's reporting requirements.

During the clinical investigation, when new information becomes available that can significantly affect a subject's future health and medical care, the Principal Investigator or his/her authorized designee, will provide this information to the subject. If relevant, the subject will be asked to confirm their continuing informed consent in writing.

5.3 SCREENING

If it is institutional practice to allow pre-screening of charts for consideration in clinical trials, sites will follow institutional policies. Ideally identification of potential patients should be done during the startup process. After IRB approval and activation, potential patients presenting at the investigational sites will be fully informed about the clinical investigation, following the established Informed Consent Process (described in section 5.2). Once a duly dated and signed ICF is obtained, the screening procedures may begin.

If a subject does not meet all inclusion criteria or meets any of the exclusion criteria, or if a subject is not implanted with both the CardioMEMS HF System or the HeartMate LVAS, the subject will not be included in the study.

5.4 POINT OF ENROLLMENT

For Group A, the subject is considered enrolled (and will count toward the analysis,) when the subject has provided written Informed Consent, has been confirmed to meet all inclusion criteria and none of the exclusion criteria. For Group B, the subject is considered enrolled (and will count toward the analysis,) when the subject has provided written Informed Consent, has been confirmed to meet all inclusion criteria and none of the exclusion criteria and has been successfully implanted with CardioMEMS. Patients who do not have a successful CardioMEMS implant after consent, will not be considered enrolled.

The Principal Investigator or delegated study personnel will record enrollment information (name of the clinical investigation, date of consent and Inclusion/exclusion information) in the patient records and complete and submit applicable case report forms (CRF) in a timely manner, but not greater than 10 days from the study visit.

Notification of enrollment to the Sponsor is considered to have occurred when the Sponsor has received the applicable CRF. For Group B, the component information CRF will be completed upon successful implant and submitted to the sponsor.

5.5 SCHEDULED PROCEDURES

The Principal Investigator is responsible for ensuring all clinical investigation data is collected as required per CIP scheduled procedures.

5.5.1 Baseline

The following baseline assessments and information will be collected after informed consent is obtained at the baseline visit. For Group A patients, these assessments will be done after consent. For Group B patients, assessments will be performed after consent and within 3 days prior to the CardioMEMS™ HF System implant.

- Medical history, physical and documentation of Inclusion/ exclusion information,
- Heart failure visit assessment including assessing and recording NYHA class, height, weight and vital signs
- Documentation of demographic information
- Documentation of HeartMate device model and CardioMEMS™ study device sensor serial number information (for group B this CRF will be completed after successful CardioMEMS implant)
- Current Medications: anticoagulation/anti platelet, and cardiovascular medications including ACE inhibitors, ARBs, beta blockers, nitrates, hydralazine, aldosterone antagonists, digoxin and diuretics. Other medications do not need to be tracked.
- Documentation of current pump parameters
- Administer Six Minute Hall Walk test (6MHWT). For Group A, CardioMEMS PA reading taken before 6MHW test (at rest) and immediately following 6MHW test (see Appendix D), ideally within one minute of test
- Administer EQ-5D-5L survey

5.5.2 Scheduled Follow-ups

Follow-up schedules are calculated from the time of baseline. Follow-up visits are scheduled at Months 1, 3, and 6 post study enrollment (two devices implanted). Sponsor Representatives will be involved in providing technical support during the Follow-up procedures.

At each visit, the following procedures must be completed:

- Document all changes in cardiovascular medications: ACE inhibitors, ARBs, beta blockers, nitrates, aldosterone antagonists, digoxin and diuretics
- Record vital signs
- NYHA Classification
- Administer EQ 5D 5L survey
- Review and document changes in pump parameters
- Administer 6MHW test per Appendix D
- CardioMEMS PA readings taken before (at rest) 6MHW test and immediately following 6MHW test, ideally within one minute of test completion (Group A and Group B)
- Emergency room visits, hospitalizations and cause for hospitalization documented
- Occurrence of protocol defined AEs (date of adverse event, determination of the seriousness and/or relation to the device, resolution of the adverse event)
- Reoperations/operative procedures pertaining to the two devices under study (HeartMate and, CardioMEMS)
- Pump Replacements/Explants/Device Exchanges (note patients are required to be withdrawn from the study at the time either device is removed)

5.6 HEMODYNAMICALLY GUIDED CLINICAL MANAGEMENT

The CardioMEMS HF System allows intermittent assessment of pulmonary artery systolic, diastolic and mean pulmonary artery pressures. Pulmonary artery pressure data from the CMEMS system, in conjunction with symptoms, weight and physical exam will be used to guide

This confidential document is the property of Abbott and shall not be reproduced, distributed, disclosed or used without the express written consent of Abbott.

clinical management of subjects following the initial CardioMEMS implant and throughout the 6-month follow-up period after enrollment.

Pulmonary artery diastolic pressure will be targeted and maintained between 8 and 15 mmHg through heart failure medical management (primarily with diuretics, nitrates, titration of HF medications), blood pressure control or LVAD speed adjustments. It is anticipated that medications can be adjusted remotely based on PA pressures observed on Merlin.net. LVAD speed adjustments are expected to be infrequent and must be done in the clinical setting. Pressure data from the CardioMEMS system will be reviewed and monitored by the clinician as frequently as is clinically indicated, but at a minimum weekly. LVAD speed changes and adjustments to HF medications will be logged throughout the follow-up period, along with the reason for the adjustment. Additionally, failure to maintain the patient in the targeted range of between 8-15 mmHg will be documented along with the reason for nonconformance.

5.6.1 Merlin.net

The Investigator or designee will review the PA pressure measurements transmitted from the home monitoring unit to Merlin.net via the Merlin.net portal. Pressure thresholds will be set to between 8 and 15 mmHg, and notifications can be set to alert the physician if pressures fall out of these ranges. These threshold notifications are intended to guide the Investigator to review the Merlin.net website and, if clinically appropriate, make a change. The Investigator or designee will review the PA pressure measurements on a weekly basis at a minimum and appropriately utilize the information to assist in the clinical management of subjects. Logins to the database will be monitored by the sponsor. Reminders will be sent to the clinical sites if no appropriate logins are observed. Clinical and technical support from the sponsor will be available to the Investigator as needed. Patients from Group A will provide consent for the sponsor to access CardioMEMS historical data collected prior to study enrollment as well as current data from the Merlin.net website. Group B will provide consent to review all Merlin.net data collected in the study.

5.7 PATIENT REPORTED OUTCOME (PRO) MEASURES

The Study Coordinator or designee will administer patient-reported outcome questionnaires. It is important the subject understands the meaning of all words and instructions in the questionnaires. The subject should be instructed to ask any questions about the questionnaires if further explanation is needed. The subject should be provided with the questionnaire as the first activity upon arrival and prior to any clinical interviewing. Once the questionnaires are completed, the Study Coordinator or designee will review for completeness to verify that all questions have been answered according to the directions provided.

The following PRO measures will be collected according to the study requirements.

5.7.1 EQ-5D-5L Questionnaire

The EQ-5D-5L Questionnaire is a standardized measure of health status developed by the EuroQol Group in order to provide a simple, generic measure of health for clinical and economic appraisal. The self-administered/electronic questionnaire consists of questions relating to mobility, self-care, usual activities, pain/discomfort, and anxiety/depression. Each dimension has 5 levels: no problems, slight problems, moderate problems, severe problems, and extreme problems. The subject is asked to indicate his/her health state by ticking (or placing a cross) in a box next to the most appropriate statement in each of the 5 dimensions and the visual analogue score. The data collected will be transferred into the Remote Data Capture (RDC) application by the coordinator and the original questionnaire kept as source. The questionnaire takes approximately five minutes to complete.

5.8 UNSCHEDULED VISITS

5.8.1 Unscheduled Office Visits

The site is required to report any associated reportable adverse events as detailed in section 8.2, as well as documentation of any medication or pump changes, and the reason for such changes, on the Heart Failure Medication Log and Pump Parameter Log CRF.

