4.3.1 Descriptive Endpoints

1. Change in Six Minute Hall Walk (6MHW) distance from enrollment to six months
2. Changes in CardioMEMS PA pressure over time
3. Percentage of days PA pressure is in the pre-specified target range
4. Changes in PA pressure before 6MHW test to after 6MHW test
5. Device malfunction (e.g. loss of performance in either device)
6. NYHA classification at baseline and each scheduled follow-up visit
7. Health related quality of life (EQ-5D-5L)
8. All-cause hospitalization rate
9. Heart failure hospitalization rate including emergency department visits, or unscheduled clinic visits for worsening HF, volume management, and/or cardiovascular medication management
10. Change in 6MHWD, NYHA class, health related quality of life, or unscheduled hospitalizations by PA pressure

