5.8.2 Emergency Room Visits or Outpatient Short Stays

All emergency room or short stays (<24 hours) visits related to heart failure will be documented and reported. Visit details must be reported to the Sponsor through the Hospitalization CRF and AE CRF through the electronic data capture system upon discovery of the event.

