6.1 ANALYSIS OF ENDPOINTS

6.1.1 Descriptive Endpoints

The following endpoints will be analyzed using descriptive statistics. Continuous variables will be summarized using numbers of subjects, mean, standard deviation, median, minimum, and maximum. Categorical variables will be summarized using frequency and percentages. Rate data will be summarized using events per patient-time.

1. Change in Six Minute Hall Walk (6MHW) distance will be summarized as change from baseline and using raw values, at 1, 3, and 6 months.
2. Changes in CardioMEMS™ PA pressure over time will include PA systolic, diastolic and mean pressures; heart rate; and cardiac output (calculated using latest algorithm for CardioMEMS) and will be summarized at baseline, throughout the study, and at 6 months.
3. Percentage of days over 6 months that PA diastolic pressure is between 8 and 15 mmHg will be summarized using the total number of days that pressures were measured as the denominator. The percentage will also be calculated at different points during the study. This endpoint will be used to assess the impact of medication and pump speed changes on PA pressures.
4. Changes in PA pressure before the 6MHW test to after the 6MHW test will be summarized at baseline (Group A only) and at 1, 3, and 6 months for both groups.
5. Device malfunction will include all instances of loss of performance of either device and will be summarized separately by device and type of loss of performance at 1, 3, and 6 months.
6. NYHA classification will be analyzed as a categorical variable and as a continuous variable at baseline, 1, 3, and 6 months. Change from baseline in NYHA will be analyzed similarly.
7. Health related quality of life (EQ-5D-5L) total score and visual analogue scale will be scored using the recommended scoring algorithms and analyzed at baseline, 1, 3, and 6 months. The change from baseline in EQ5D-5L will be analyzed similarly.
8. All-cause hospitalization rate will be summarized over 6 months in units of events per patient-time.
9. Heart failure hospitalization rate including emergency department visits, or unscheduled clinic visits for worsening HF, volume management, and/or cardiovascular medication management will be summarized over 6 months in units of events per patient-time.
10. Change in 6MHWD, NYHA class, EQ-5D-5L, or unscheduled hospitalizations will be analyzed descriptively according to subgroups based on PA diastolic pressure.

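### Endpoint 9 counts unscheduled clinic visits, but no collection rule in the protocol requires such a visit, its date or its reason to be recorded, so this component may be under-counted

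*Combined protocol and SAP*

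**What the plan says.** **The endpoint.** Section 4.3.1, item 9 defines a "Heart failure hospitalization rate including emergency department visits, or unscheduled clinic visits for worsening HF", with volume and cardiovascular medication management as further qualifying reasons. Section 6.1.1, item 9 repeats the composite, ending "unscheduled clinic visits for worsening HF, volume management, and/or cardiovascular medication management will be summarized over 6 months", in events per patient-time.

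**Unscheduled office visits (5.8.1).** Two things are required. The first is adverse events: "The site is required to report any associated reportable adverse events as detailed in section 8.2". The second is "documentation of any medication or pump changes, and the reason for such changes, on the Heart Failure Medication Log and Pump Parameter Log CRF".

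**Emergency visits and short stays.** Section 5.8.2 states: "All emergency room or short stays (<24 hours) visits related to heart failure will be documented and reported". Details go on the Hospitalization CRF and the AE CRF. The checklist for each scheduled follow-up in section 5.5.2 has: "Emergency room visits, hospitalizations and cause for hospitalization documented".

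**Hospitalizations (5.8.3).** All are captured, with reasons.

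**Medication changes (5.6).** The protocol anticipates that "medications can be adjusted remotely based on PA pressures observed on Merlin.net". LVAD speed changes, by contrast, must be made in the clinical setting.

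**The concern.** A rate in events per patient-time needs a count of events, and each event has to be dated and classified by reason. For admissions the protocol asks for this. For emergency visits it mostly does. For unscheduled clinic visits it asks for possible consequences of the visit (an adverse event, a drug change, a pump change) but not for the visit.

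A site that follows section 5.8.1 to the letter can therefore omit events that endpoint 9 is meant to count. Unrecorded visits may be hard to recover afterwards. The study is descriptive and is meant to inform the design of later trials. Section 6 also says that any p-values will help identify endpoints sensitive to the benefit of monitoring. A heart failure event rate with an unknown shortfall in one component is a poor planning figure for that purpose.

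**Working it through.** The plan gives no event rate for endpoint 9, so there is no figure to reproduce. The check sets the endpoint against each route by which a clinic visit could reach the database, then illustrates the size.

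**Step 1: direct routes.**
- Section 5.8.1: no visit record, date or reason is required.
- Section 5.5.2 checklist: emergency room visits and hospitalizations are listed, clinic visits are not.
- Table 2, As occurs column: adverse events, hospitalizations, device malfunctions and medication changes have rows, unscheduled clinic visits do not.
- Section 8.3, records to be supplied on request: adverse events, ER visits, short stays and admissions are named, clinic visits are not.
- Appendix B: HF hospitalization is an admission of at least 24 hours with HF on the discharge diagnosis, so it does not define a countable clinic visit.

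**Step 2: indirect routes.**
- *Adverse events (8.2).* Worsening heart failure is on the list, but events are reportable only if considered possibly or likely related to a device, to study procedures or to treating to target. A visit for progression considered unrelated is not reportable.
- *Medication log.* It holds the reason for each change, but section 5.6 expects remote changes and nothing requires an entry to be marked remote or in clinic. Counting entries as visits would include remote changes; ignoring them would lose real visits.
- *Pump log.* A speed change does show an in-person encounter, but such changes are expected to be infrequent.
- *Out-of-range rationale (4.1, 5.6).* This is triggered by the pressure reading, not by a visit.

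What remains without any countable record is mainly the symptomatic visit with pressure in range, no medication or pump change and no related adverse event. Visits with only a medication change leave an entry that cannot be told apart from a remote change.

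**Step 3: emergency visits.** Section 5.8.2 is limited to HF-related visits, while endpoint 9 also names volume and cardiovascular medication management. Section 5.5.2 has no such limit, but asks for the cause of hospitalization and not clearly for the cause of an ER visit. A visit for low volume could thus be listed without a reason that can be classified.

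**Step 4: illustration of size.** Maximum exposure is 100 subjects × 0.5 year = 50 patient-years (section 4.1). Let *s* be the share of true endpoint 9 events that are unscheduled clinic visits, and *c* the share of those visits identifiable from the CRFs. Both are assumptions; the other components are taken as fully captured.

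Recorded rate / true rate = (1 − *s*) + *s* × *c* = 1 − *s*(1 − *c*)

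| *s* | *c* = 0 | *c* = 0.5 | *c* = 1 |
|---|---|---|---|
| 10% | 0.90 | 0.95 | 1.00 |
| 20% | 0.80 | 0.90 | 1.00 |
| 30% | 0.70 | 0.85 | 1.00 |
| 50% | 0.50 | 0.75 | 1.00 |

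For example, with *s* = 0.5 and *c* = 0.5: 1 − 0.5 × 0.5 = 0.75, a shortfall of 25%.

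**The case against.** The strongest reply is that much of what happens at an unscheduled visit is recorded. A medication or pump change is logged with its reason, a patient left outside the target range needs a documented rationale, and events related to treating to target are reportable. The CRFs themselves are not in the documents, so a log or visit form may already hold an encounter field. Finally, this is one component of one of ten descriptive endpoints in a feasibility study with no hypothesis tests and no success criteria.

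These points limit the finding without removing it. None of the required records is a visit count, and if a CRF field does exist, the protocol should still instruct sites to use it. The descriptive status lowers the stakes, but in such a study the summaries are the product.

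Three stronger readings are tempting, and the documents do not support them:
- *Emergency visits are not captured.* They largely are: section 5.8.2 requires all HF-related ones, section 5.5.2 asks about ER visits at every follow-up, and section 8.3 gives access to their records. Dizziness and hypovolemia are also on the adverse event list in section 8.2, if related. Only the gap in step 3 remains.
- *Endpoint 10 is biased as well.* Endpoint 10 uses unscheduled hospitalizations, not clinic visits, and section 5.8.3 captures all hospitalizations with reasons.
- *The loss can be sized from the background figures.* Section 2 cites about 80% of LVAD patients re-hospitalized within a year of implant, with 10% of readmissions for pressure/volume management or worsening HF. These describe admissions. They say nothing about the number of unscheduled clinic visits or the share left unrecorded.

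**Conclusion.** The concern holds for unscheduled clinic visits. The collection rules as written do not ensure the count that endpoint 9 needs, and the clinic-visit component may be under-counted. A reader might infer that the reported rate will be wrong. That goes too far, because the CRFs are not available and there is no loss if they make every visit identifiable (*c* = 1).

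Lost visits push the rate downward. The size cannot be derived from the documents. Under the assumption that clinic visits make up 10–50% of true events, the shortfall is 5–25% when half are identifiable and 10–50% when none are. These ranges also assume that admissions and emergency visits are completely captured and that no remote change is counted as a visit.

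The gap for emergency visits and short stays is narrower: it concerns which reasons are covered and recorded. The change is worth making because it is cheap and data not collected may be hard to recover, but the rest of the plan does not depend on it.

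**What to change.** - **5.8.1:** require every unscheduled clinic visit to be recorded with its date and primary reason (worsening HF, volume, cardiovascular medication, other), as an encounter type on the existing Hospitalization CRF.
- **5.5.2 and Table 2:** add unscheduled clinic visits to the checklist at Months 1, 3 and 6, and add a row in the As occurs column.
- **5.8.2:** extend reporting of ER visits and short stays to all endpoint 9 reasons, with the cause recorded, so that it agrees with 5.5.2 and 6.1.1.
- **Medication log:** mark each entry as remote or in clinic.
- **6.1.1, item 9:** report hospitalizations, emergency visits and clinic visits separately as well as combined, so that a weakness in one component is visible.

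The cost is a wording change to the protocol, a small CRF edit, one extra mark per medication-log entry and one short entry per unscheduled visit. Patient management is not affected.
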